### 13.2. Deriving and Summarizing Pharmacokinetic Parameters

All PK parameter displays will be based on PK parameter population.

As data permit, the following pharmacokinetic parameters will be determined from the plasma concentration-time data for GSK2849330. The pharmacokinetic parameters will be calculated by standard non-compartmental analysis according to current working practices and using WinNonlin Professional Version 6.3 or higher. All calculations of non-compartmental parameters will be based on actual sampling times.

- 1. The first occurrence of the maximum observed plasma concentration determined directly from the raw concentration-time data (Cmax).
- 2. The time at which Cmax is observed will be determined directly from the raw concentration-time data (tmax).
- 3. The apparent terminal elimination half-life  $(t_{1/2})$  obtained as the ratio of  $\ln 2/\lambda z$ , where  $\lambda z$  is the terminal phase rate constant estimated by linear regression analysis of the log transformed concentration-time data
- 4. The time to reach the last quantifiable concentration (tlast)
- 5. The area under the plasma concentration-time curve to the last quantifiable concentration (AUC(0-t)) determined using the linear trapezoidal rule for increasing concentrations and the logarithmic trapezoidal rule for decreasing concentrations.
- 6. The AUC to a fixed nominal time (AUC(0-168)) will be calculated using the linear trapezoidal rule for increasing concentrations and the logarithmic trapezoidal rule for decreasing concentrations.
- 7. The AUC over the dosing interval (AUC( $0-\tau$ )), where  $\tau$  is the dosing interval, will be calculated using the linear trapezoidal rule for increasing concentrations and the logarithmic trapezoidal rule for decreasing concentrations.
- 8. The AUC extrapolated to infinity (AUC(0- $\infty$ )) will be calculated, where data permit, as the sum of AUC(0-t) and Ct/ $\lambda z$ , where Ct is the observed [insert matrix] concentration of the last quantifiable time-point and  $\lambda z$  is the terminal phase rate constant obtained from the log-linear regression analysis.
- 9. The percentage of AUC( $0-\infty$ ) obtained by extrapolation (%AUC $\infty$ ex) will be calculated as the ratio of [AUC( $0-\infty$ ) minus AUC(0-t)] to AUC( $0-\infty$ ) X 100.

- 10. C $\tau$ : pre-dose (trough) concentration at the end of the dosing interval on the specified days (Only for Days 8, 15 and 22 where available).
- 11. Clearance (CL) after single dose for iv administration (CLiv)  $CL = Dose/AUC(0-\infty)$

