The proposed starting dose is 1.4 mg/kg, administered once-weekly. According to ICHS9 guidance, calculating a starting dose based on HNSTD/6 in the most relevant species (cynomolgous monkey) yields a starting dose of \sim 16 mg/kg/wk. We selected a more conservative starting dose of 1.4 mg/kg/wk, slightly above the MABEL calculated from tumor xenograft studies, which in turn suggests that clinical activity may be observed at dose levels of 1.2 mg/kg and higher.

Table 3 Dose Levels

Cohort	Dose	N Dose Escalation Cohorts	N PK-PD Cohorts
1	1.4 mg/kg weekly	1 (minimum)	up to 3
2	3 mg/kg every 2 weeks	3 (minimum)	up to 3
3	10 mg/kg every 2 weeks	3 (minimum)	up to 3
4	30 mg/kg every 2 weeks	3 (minimum)	up to 3
5	30 mg/kg weekly (optional change to every 2 weeks after 24 weeks of treatment)	3 (minimum)	up to 3
Additional optional cohorts may be enrolled at different dose levels and intensities			

Maximum Proposed Dose

The maximum proposed dose of 30 mg/kg for weekly, bi-weekly or every three week dosing was selected based on PK-PD extrapolations which predict target engagement > 90% and tumor saturation should be achieved at or below this dose, and based on practical considerations (e.g., drug product supply and production capacity) Emerging PK, safety and tolerability data may cause the proposed maximum dose to be adjusted downward (see Section 3.3 for details of the N-CRM model assessment of safety data).

Dose Escalation

The proposed dose escalation scheme is based on a half-log step size, with the exception of the 30 mg/kg/wk dose and the nominal doses shown in Table 3 represent the maximum dose which may be selected. The study team, in discussion with the investigator(s), may select other doses or alternative schedules besides those shown, based on emerging safety, tolerability, PK and/or PD data.

Dosing Interval

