13.5. Treatment Comparisons

13.5.1. Primary Comparisons of Interest

Several dose levels and regimens of GSK2849330 are being investigated. No formal comparisons will be performed regarding differences between the dose levels. Safety, PK, PD biomarker, and clinical benefit summaries will be provided by dose level of GSK2849330.

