# 3. STUDY DESIGN

This is a Phase I, FTIH, open-label, multi-center, dose-escalation study of the anti-HER3 antibody, GSK2849330, in subjects with advanced solid tumors expressing HER3 (2+ or 3+). The study will be conducted in two parts as depicted below.

Part 1
Dose Escalation Cohorts
To determine the safety, tolerability, PK and preliminary PD of GSK2849330, in support of selection of the recommended dose(s) and regimen(s) for further exploration in subjects with advanced solid tumors with HER3 expression
PK/PD Cohorts
Subjects that agree to give pre- and on- treatment tumor biopsies will be enrolled in the PK/PD cohorts to support selection of the recommended dose(s) and regimen(s) for Part 2. Up to 3 subjects with evaluable pre- and on-treatment tumor biopsies will be enrolled at each dose level after that dose is determined tolerable.
$\downarrow$
Part 2
Expansion Cohort
To determine safety and preliminary evidence of clinical benefit of GSK2849330, and to
further evaluate the PK and PD of GSK2849330 at the recommended Part 2 dose(s) and
regimen(s) in subjects with selected HER3 or HER 3 and NRG1 expressing tumor types.

**Dose Escalation Cohorts** will identify the MTD on the fixed-dose dosing schedule using an accelerated titration scheme followed by Neuenschwader-Continuous Reassessment Method (N-CRM).

The proposed starting dose and schedule of GSK2849330 is 1.4 mg/kg weekly given for 28 days. The single subject in Cohort 1 only must complete a full 28 days of dosing, and the safety and PK data will be reviewed.

The planned dose and schedule for Cohort 2, 3 and 4 are corresponding 3 mg/kg every 2 weeks, 10 mg/kg every 2 weeks and 30 mg/kg every 2 weeks given for 28 days. Starting with Cohort 2, the dose escalation will continue using N-CRM method with 3 subjects in each cohort. In cohort 2 through 4, the first subjects in each cohort will begin dosing and

be observed for at least 24 hours prior to dosing the rest of the that cohort at same dose level.

Additional subjects may also be enrolled at any specified dose level to further characterize the safety. Additional doses and schedules and loading doses may be explored based on emerging safety, PK and PD data.

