# 13.3. Statistical Analyses of Pharmacokinetic Data

Statistical analyses of pharmacokinetic parameters will be responsibility of Oncology, Clinical Statistics, GSK. Statistical analysis of the exploratory compartmental PK parameters data will be the responsibility of CPMS, Quantitative Sciences, GSK.

PK data will be presented in graphical and/or tabular form and will be summarized descriptively.

For all statistical analyses, AUC( $0-\infty$ ), AUC(0-t), AUC( $0-\tau$ )), AUC(0-168), t1/2, and Cmax will be separately analysed after loge-transformation.

Individual plasma PK parameters values as well as descriptive summary (mean, SD, median, minimum, maximum, geometric mean, and the standard deviation, 95% confidence interval (CI) of log-transformed parameters (if applicable) by dose group will be reported.

Pre-dose trough concentration (C  $\tau$ ) samples obtained immediately before the morning dose on Days 8, 15, and 29 will be presented in a listing and will be summarized descriptively by dose.

Box plot figures will be generated based on dose normalized data for Cmax and AUC(0- $\infty$ ), AUC(0-168), and AUC(0- $\tau$ )) as a function of the dose administered.

Individual and Box Plot of Plasma GSK2636771 Pre-Dose Concentration Data on Day 8, 15 and 29 by Dose Cohort in Part 1 will be provided.

Statistical analysis of Cmax and AUC may be performed as appropriate dose proportionality.

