# 19.1.5. Pharmacokinetic Figures and Tables

# **Figures**

Figure No.	Population	IDSL No. / Example Shell	Title	Programming Notes	Deliverable Priority
13.1	PK parameter	PK16a, pkcf1p	Individual Plasma GSK2849330 Concentration-Time Plots by Dose Cohort in Part 1 (Linear and Semi-log)		SAC
13.2	PK parameter	РК17, РКСF2	Mean (± SD) GSK2849330 Plasma Concentration-Time Plots by Dose Cohort in Part 1 (Linear and Semi-log)		SAC
13.3	PK parameter	PK18, pkcf3	Median GSK2849330 Plasma Concentration-Time Plots by Dose in Part 1 (Linear and Semi-log)		SAC
13.4	PK parameter		Individual and Box Plot of Dose-Normalized Plasma GSK2636771 PK Parameters by Dose Cohort in Part 1	For Cmax, AUC(0-∞), AUC(0-168), and AUC(0-т) arenv/arprod/gsk263 6771/p3b115717/sac /drivers/f_pkp_box_s ingle.sas	SAC
13.5	PK parameter		Individual and Box Plot of Plasma GSK2636771 Pre-Dose Concentration Data on Day 8, 15 and 29 by Dose Cohort in Part 1	arenv/arprod/gsk263 6771/p3b115717/sac /drivers/f_pkc_box_p re.sas	SAC

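### The SAP labels Day 8 (and, in 13.2, Day 22) an end-of-interval trough for all Part 1 cohorts, although these days fall mid-interval in the every-2-week cohorts

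*SAP*

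**What the plan says.** **Trough days.** SAP 13.2, item 10, defines Cτ as the "pre-dose (trough) concentration at the end of the dosing interval on the specified days (Only for Days 8, 15 and 22 where available". SAP 13.3 lists and summarises Cτ by dose from samples "obtained immediately before the morning dose on Days 8, 15, and 29". Figure 13.5 in SAP 19.1.5 shows "Pre-Dose Concentration Data on Day 8, 15 and 29 by Dose Cohort in Part 1". The first list has Day 22 where the other two have Day 29, and none distinguishes weekly from every-2-week dosing.

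**Dosing and sampling.** SAP section 3 gives Cohorts 2 to 4 as "3 mg/kg every 2 weeks, 10 mg/kg every 2 weeks and 30 mg/kg every 2 weeks given for 28 days". In Protocol Tables 7 and 9 the every-2-week infusions are on Days 1, 15 and 29, with a PK sample but no infusion on Day 8. Protocol 7.4 schedules no Day 22 sample for dose-escalation Cohorts 1 to 4. It does schedule one for the PK/PD cohorts and for cohorts enrolled under Amendment 1, which are sampled weekly to Day 57.

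**Use.** Protocol 13.7.3.2 says that the Cτ samples will be used to judge whether steady state has been reached.

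**AUC.** SAP 13.3 states: "Box plot figures will be generated based on dose normalized data". These plots cover Cmax, AUC(0-∞), AUC(0-168) and AUC(0-τ), set against dose.

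**The concern.** A trough is the concentration just before the next dose. On Day 8 an every-2-week subject is halfway through the interval and receives nothing that day, so the value is higher than the trough. If the plan is followed as written, the report will show this value as Cτ for Cohorts 2 to 4, next to genuine troughs from the weekly cohorts.

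The damage is to the steady-state check. That check reads successive troughs within a cohort, and a sequence that starts with a mid-interval value does not show accumulation correctly. Under the 13.2 list, the every-2-week cohorts keep only one real trough (Day 15), which is too few to judge steady state at all.

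A secondary question concerns AUC(0-τ). τ is 168 h in the weekly cohorts and 336 h in the others, and the SAP does not say which dose the parameter comes from.

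**Working it through.** **The plan's own figure.** Protocol 3.6.3 gives a catabolic half-life of 172 h from V1/CL. Check: ln 2 × 2830/11.4 = 172.07 h, which agrees.

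**Inputs.** Half-lives: 119 h and 134 h (Protocol Table 5, at 3 and 10 mg/kg), 172 h, and 240 to 336 h (the 10 to 14 days expected after repeated dosing). Model parameters (Protocol Table 6): CL 11.4 mL/h, V1 2830 mL, VM 198 µg/h, KM 0.513 µg/mL, Q 79.0 mL/h, V2 3420 mL. Body weight: 60 kg, the protocol's scaling weight. 75 and 90 kg are assumptions used to show a range.

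**Day 8 against Day 15, mono-exponential.** C168/C336 = 2^(168/t½):

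| t½ (h) | 119 | 134 | 172 | 240 | 336 |
|---|---|---|---|---|---|
| Ratio | 2.66 | 2.38 | 1.97 | 1.62 | 1.41 |

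**The same under the protocol's model.** This is a two-compartment model with saturable loss VM·C2/(KM + C2) from the peripheral compartment, a 1-hour infusion, and numerical solution. As a check, AUC(0-336) at 10 mg/kg comes to 23,362 h·µg/mL at 60 kg and 29,517 at 75 kg, against 28,100 in Table 5. Results in µg/mL at 60 kg:

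| Dose every 2 weeks | Day 8 | Day 15 | Day 29 | Day 8/Day 15 | Day 29/Day 8 | Day 29/Day 15 |
|---|---|---|---|---|---|---|
| 3 mg/kg | 15.8 | 7.6 | 11.4 | 2.1 | 0.72 | 1.50 |
| 10 mg/kg | 61.6 | 41.6 | 64.4 | 1.5 | 1.04 | 1.55 |
| 30 mg/kg | 192.8 | 139.3 | 216.5 | 1.4 | 1.12 | 1.55 |

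At 75 and 90 kg, Day 8/Day 15 is 1.9 and 1.7 at 3 mg/kg, and stays at 1.4 to 1.5 at 10 and 30 mg/kg.

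**Effect on the steady-state reading.** Take t½ = 172 h, mono-exponential, with the initial concentration set to 1:

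- Day 8 = 2^(−168/172) = 0.508.
- Day 15 = 0.508² = 0.258.
- Day 29 = 0.258 + 0.258² = 0.325.

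Read as troughs, Day 29 is 36% below Day 8 (0.325/0.508 = 0.64). The true trough has risen 26% since Day 15 (0.325/0.258 = 1.26). The apparent fall is not universal. At t½ = 336 h, Day 29 is 0.5 + 0.25 = 0.75 against 0.707 on Day 8. In the model, the fall appears at 3 mg/kg (ratio 0.72). At 10 and 30 mg/kg the Day 8 to Day 29 comparison looks nearly flat (1.04 and 1.12) while the true trough rises 1.55-fold.

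**AUC(0-τ) at 30 mg/kg, 60 kg.**

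- First dose: 72,612 over 336 h against 44,941 over 168 h, a ratio of 1.62. It is also 1.62 at 75 and 90 kg. The mono-exponential ratio, 1 + 2^(−168/t½), runs from 1.38 to 1.71 for half-lives of 119 to 336 h.
- First dose, AUC(0-168): the same 44,941 in both regimens, a ratio of 1.00.
- Steady state: 154,977 (weekly) against 152,066 (every 2 weeks), a ratio of 1.02. Per week, exposure is 154,977 against 76,033, a ratio of 2.04.

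**The case against.** **The definition may exclude Day 8 by itself.** It asks for the end of the interval, SAP 13.3 asks for a sample before a dose, and a non-dosing Day 8 meets neither. SAP 13.2 also adds an availability qualifier, and each day is named in Figure 13.5 and not pooled. Part of this stands: the Day 15 value will be visible under its own label. But the Day 8 samples exist in these cohorts, so the qualifier removes nothing, and 13.3 and the figure carry no such qualifier. Nor can the pre-dose label act as a filter. The Table 9 footnote applies it to Day 4 and Day 8 samples in the every-2-week PK/PD cohorts.

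**Day 22 has limited reach.** This stands. It appears only in 13.2 and is not scheduled for dose-escalation Cohorts 1 to 4.

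**The upper ratios lean high.** This stands in part. The 119 h half-life comes from one of three subjects, and the protocol's model gives smaller ratios.

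**The AUC point is narrower than it looks.** A reader might infer that exposure cannot be compared between regimens. The documents do not support that. AUC(0-168), Cmax and AUC(0-∞) are in the same box plots, and the columns in SAP 7.1 separate dose from frequency. Protocol 13.7.3.1 ties AUC(0-τ) to repeat dosing, where its dose-normalised value at 30 mg/kg hardly depends on τ. Against this, Cohorts 2 to 4 on the base sampling schedule have post-infusion samples only after the first dose, so for them the parameter may in practice come from that dose.

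**Conclusion.** The point holds for the trough displays. Without a split by regimen, a mid-interval value is reported as Cτ for the every-2-week cohorts, and the SAP's lists of days conflict. The overstatement relative to the first-dose Day 15 trough is about 1.4 to 2.1 times under the protocol's model at 60 kg, and 1.4 to 2.7 times mono-exponentially. Depending on half-life and dose, the true rise to Day 29 is shown as a fall or as a near-plateau, and either misleads the steady-state check.

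The sizes rest on preliminary parameters from five subjects and on assumed body weights. The 336 h half-life is a repeated-dosing value applied to a first dose. That Day 8 lies above the Day 15 trough depends on none of this.

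The AUC(0-τ) point is a request for clarification. The roughly 1.6-fold difference at 30 mg/kg arises only if the parameter is taken from the first dose.

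A reader might also infer that these displays drive the choice of regimen. The documents do not support that. The displays belong to the final analysis after database freeze (SAP 4.2), SAP 7.1 already lists Part 2 at 30 mg/kg, and Protocol 13.6.1 makes safety and tolerability the main driver of escalation. Protocol 13.5.1 adds: "No formal comparisons will be performed regarding differences between the dose levels". The consequence is a misleading descriptive report.

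**What to change.** 1. In SAP 13.2, define the Cτ days by regimen. Weekly: Days 8, 15, 22 and 29 where sampled (Cohort 1 has no scheduled Day 22 sample). Every 2 weeks: Days 15 and 29.
2. Use the same list in SAP 13.3 and Figure 13.5.
3. Keep the Day 8 and Day 22 samples of the every-2-week cohorts, labelled as mid-interval concentrations, and leave them out of the steady-state assessment.
4. State which dose AUC(0-τ) refers to. If it is the first dose, use the already planned AUC(0-168) for between-regimen plots and show AUC(0-τ) within regimen.

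The cost is a few lines in SAP 13.2 and 13.3 and changes to two figure specifications (13.4 and 13.5). No new samples or analyses are needed.

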7.4. Pharmacokinetics

For subjects enrolled in Part 1, dose escalation Cohorts 1-4, blood samples for analysis of GSK2849330 concentrations will be collected on Day 1: pre-dose and at 1 hour and 6 hours after the end of infusion and at Day 8, Day 15, and Day 29 after the first dose of GSK2849330. If a subject's duration of infusion is 3 hours or longer, the 6-hour time point is optional. On days of dosing, the sample will be drawn pre-dose. Additionally the first subject in Cohort 1 will have PK samples taken at 24 hour (Day 2) and 72 hour (Day 4) after the end of infusion.

For cohorts enrolled under Amendment 1 of this protocol, more frequent PK samples will be collected on Day 1: pre-dose and at 1 hour, 6 hours and 24 hours after the end of infusion;. Pre-dose samples will also be collected on Day 4, Day 8, and weekly through Day 57 with additional 1 hour post-dose samples collected on Days 29 and 57. Pre-dose samples will also be collected on Day 71, Day 85, and every 12 weeks thereafter.

For all subjects in the Part 1 PK/PD cohorts, blood samples for analysis of GSK2849330 concentrations will be collected on scheduled dosing Days 1: pre-dose and at 1 hour, 6 hours and 24 hours after the end of infusion. Pre-dose samples will also be collected on Day 4, Day 8, and weekly through Day 57 with additional 1 hour post-dose samples collected on Days 29 and 57. Pre-dose samples will also be collected on Day 71, Day 85 and every 12 weeks thereafter.

For the molecularly defined tumor histology groups in Part 2, blood samples for analysis of GSK2849330 concentrations will be collected on Day 1: pre-dose and at 1 hour after the end of infusion; and pre-dose on Day 15, Day 29, Day 43, Day 57, Day 71, Day 85, and every 12 weeks thereafter.

For all subjects (Part 1 and Part 2), if treatment continues beyond 1 year, samples will be collected every 24 weeks. An additional PK sample will also be taken at the Follow-up visit (28 days after the last dose of study treatment), and/or the Post study visit (45 days or 5 half-lives [whichever is longer] after the last dose of study treatment). Unless stated otherwise, on days of dosing PK samples will be drawn pre-dose.

See the Time and Events Tables Section 7.1 and the SPM for additional details on the PK sample timing.

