# 7.1. Data Display Treatment and Other Subgroup Descriptors

Treatment groups with the same dose and the same administration frequency will be combined in final analyses as displayed in the table below. All data will be summarized or listed by the treatment group except PK concentration data, which will be listed by part and dose cohort.

Treatment	Treatment Description	Treatment Label / Column Header
Code		
1	Part 1 DE Cohort: 1.4 mg/kg weekly	Part 1 Cohort: 1.4 mg/kg weekly
2	Part 1 DE Cohort: 3 mg/kg every 2 weeks	Part 1 Cohort: 3 mg/kg every 2 weeks
3	Part 1 DE & PK/PD Cohort: 10 mg/kg every 2 weeks	Part 1 Cohort: 10 mg/kg every 2 weeks
4	Part 1 DE & PK/PD Cohort: 30 mg/kg every 2 weeks	Part 1 Cohort: 30 mg/kg every 2 weeks
5	Part 1 DE & PK/PD Cohort: 30 mg/kg weekly	Part 1 Cohort: 30 mg/kg weekly
6	Part 1 PK/PD Cohort: 3 mg/kg weekly	Part 1 Cohort: 3 mg/kg weekly
7	Part 2 Expansion Cohort: 30 mg/kg	Part 2 Cohort: 30 mg/kg

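### SAP 13.2 and 13.3 apply one set of non-compartmental rules to Part 1 subjects with different first-dose sampling, so AUC(0-168), AUC(0-tau) and first-dose clearance are not comparable across the planned displays

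*SAP*

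**What the plan says.** **Sampling.** Protocol 7.4 gives escalation Cohorts 1-4 samples "pre-dose and at 1 hour and 6 hours after the end of infusion and at Day 8, Day 15, and Day 29". Only the first Cohort 1 subject also has 24 h and 72 h. PK/PD cohorts are sampled "pre-dose and at 1 hour, 6 hours and 24 hours after the end of infusion", followed by this: "Pre-dose samples will also be collected on Day 4, Day 8, and weekly through Day 57". Cohorts enrolled under Amendment 1 have the same richer schedule. Protocol Table 7 (escalation, every 2 weeks) is the sparse schedule; Tables 8, 9 and 10 are rich.

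**Pooling.** SAP 7.1 states: "Treatment groups with the same dose and the same administration frequency will be combined in final analyses". Codes 3 (10 mg/kg) and 4 (30 mg/kg), both every 2 weeks, combine escalation and PK/PD subjects. Code 2 (3 mg/kg every 2 weeks) is escalation only, and code 6 (3 mg/kg weekly) is PK/PD only.

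**Derivation and display.** SAP 13.2 uses the linear trapezoid for rising and the logarithmic trapezoid for falling concentrations, and a log-linear regression for lambda-z. Its list ends with "Clearance (CL) after single dose for iv administration (CLiv", set to dose over AUC(0-inf). It names no time window, minimum number of points or limit on extrapolation. The extrapolated percentage is derived, but no rule uses it. SAP 13.3 says "Box plot figures will be generated based on dose normalized data for Cmax" and three AUC measures: AUC(0-inf), AUC(0-168) and AUC(0-tau). These are Figure 13.4. A dose-proportionality analysis is optional.

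**The concern.** A trapezoidal AUC depends on where the samples lie. This antibody distributes over the first days, and the sparse schedule has no sample from 6 h to Day 8. A logarithmic trapezoid across that gap joins an early high value to a late low one by a single exponential, which lies above a curve that falls quickly and then slowly.

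If schedules differ between columns, or within one pooled column, part of the displayed difference comes from sampling and not from the drug. Separately, weekly subjects are re-dosed at 168 h. Their first-dose AUC(0-inf) and CL therefore rest on a shorter observed profile than those of every-2-week subjects.

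At stake is the reported description of exposure by dose and regimen, a secondary endpoint in both parts.

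**Working it through.** **Plan's own figure.** Protocol 3.6.3 gives a catabolic half-life of 172 h. From Table 6: (2830 / 11.4) x ln 2 = 172.07 h. It reproduces.

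**Model.** Table 6: CL 11.4 mL/h, V1 2830 mL, Q 79.0 mL/h, V2 3420 mL, VM 198 ug/h, KM 0.513 ug/mL, 1 h infusion, saturable loss from the peripheral compartment:
- V1 dC1/dt = infusion rate - CL C1 - Q (C1 - C2)
- V2 dC2/dt = Q (C1 - C2) - VM C2 / (KM + C2)

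Body weight is not given. I assume 70 kg; 60 and 80 kg give similar results.

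**Sampling, hours from start of infusion.** Sparse every 2 weeks: 2, 7, 168, 336. Rich every 2 weeks: 2, 7, 25, 72, 168, 336. Rich weekly: 2, 7, 25, 72, 168.

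**Rules.** Falling segment: (t2 - t1)(Ca - Cb) / ln(Ca / Cb). AUC(0-inf) = AUC(0-t) + Ct / lambda-z. CL = dose / AUC(0-inf).

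**AUC divided by dose (h*ug/mL per mg/kg), one noise-free profile per dose:**

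| Dose, measure | Model | Sparse | Rich |
|---|---|---|---|
| 3 mg/kg, 0-168 | 1659 | 2071 (+25%) | 1681 (+1.3%) |
| 10 mg/kg, 0-168 | 1729 | 2179 (+26%) | 1755 (+1.5%) |
| 30 mg/kg, 0-168 | 1749 | 2210 (+26%) | 1776 (+1.5%) |
| 3 mg/kg, 0-336 | 2460 | 2858 (+16%) | 2467 (+0.3%) |
| 10 mg/kg, 0-336 | 2747 | 3194 (+16%) | 2770 (+0.8%) |
| 30 mg/kg, 0-336 | 2831 | 3290 (+16%) | 2857 (+0.9%) |

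For every-2-week dosing, AUC(0-336) is AUC(0-tau).

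**Effect on the planned displays:**
- Code 2 against code 6, AUC(0-168): true ratio 1.00; computed 2071 / 1681 = 1.23.
- 30 mg/kg weekly (rich) against 3 mg/kg every 2 weeks (sparse): true 1749 / 1659 = 1.05; computed 1776 / 2071 = 0.86. The direction reverses.
- A code 3 column with equal numbers on each schedule: geometric mean error sqrt(1.26 x 1.015) = 1.13.

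**AUC(0-inf) and CL at 30 mg/kg** (dose 30 x 70 = 2,100 mg; model AUC(0-inf) 155,658 h*ug/mL, CL 13.5 mL/h). The SAP fixes no lambda-z points, so two choices are shown:

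| Schedule | Last 3 points: t1/2, CL | From 24 h on: t1/2, CL |
|---|---|---|
| Weekly, rich | 177 h, 19.0 | 177 h, 19.0 (same points) |
| Every 2 weeks, rich | 345 h, 12.6 | 259 h, 14.3 |
| Every 2 weeks, sparse | 174 h, 15.0 | 364 h, 11.4 |

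For example, 2,100,000 / 110,808 = 19.0 weekly and 2,100,000 / 167,163 = 12.6 rich every 2 weeks (12.5 if Day 4 is placed at 73 h). With the last 3 points the extrapolated share is 52% weekly, 49% rich and 29% sparse.

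**Sensitivity** (10 and 30 mg/kg; Q x0.62-1.38, V2 x0.73-1.27, CL x0.5-2, VM x1-2). The sparse/rich ratio stays at 1.19-1.28 for AUC(0-168) and 1.12-1.19 for AUC(0-336). The weekly/rich every-2-week ratio of AUC(0-inf), last 3 points, is 0.50-0.96.

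**Check against Table 5, 10 mg/kg.** Model concentration 1 h after infusion is 236 against an observed Cmax of 234 ug/mL. Sparse AUC(0-336) is 22,400 (50 kg) to 31,900 (70 kg) against 28,100. The half-life does not match: 308 h from Day 8 to Day 15, against 134 h. Parameter sets with a Day 8-15 half-life of 130-154 h still give a sparse/rich AUC(0-168) ratio of about 1.20.

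**The case against.** The best defence is that SAP 13.2 and 13.3 describe a final analysis after database freeze, with no formal comparison (SAP 4.2, 7). Parameters are derived only where the data allow, and the PK Parameter Population requires valid ones. The extrapolated percentage is derived, individual values are listed and plotted, and actual sampling times are used. A population analysis is foreseen in 13.4. The model rests on five subjects at 10 mg/kg or below, with relative standard errors near 40% on CL and VM.

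Much of this stands: it limits the consequence and makes the sizes illustrative. It does not remove the artefact. Actual times cannot replace absent samples, the validity conditions carry no threshold, and the population analysis is conditional. The SAP refers to current working practices, but whether these set a limit cannot be seen.

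Four stronger readings are tempting and not supported:
- A reader might infer that sparse sampling shifts half-life or CL in a known direction among every-2-week subjects. It does not: the order reverses between the two lambda-z choices above, and the second is the one Protocol Table 5 labels, with windows starting at 24 h.
- A reader might infer a fixed 50% excess in weekly clearance. Against rich every-2-week subjects it is 19.0 / 14.3 = 1.33 to 19.0 / 12.6 = 1.51, depending on the window, and code 4 may be a mixed column.
- A reader might infer that these outputs choose the regimen. SAP 4.1 gives escalation decisions a separate ongoing review using nominal times, and SAP 7.1 already lists Part 2 at 30 mg/kg.
- A reader might infer that the differences are all artefact. The schedule effect adds to real ones, such as target-mediated nonlinearity and between-subject variation.

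**Conclusion.** The point holds for AUC(0-168) and AUC(0-tau). Sparse sampling alone raises AUC(0-168) by about 25-26% and every-2-week AUC(0-tau) by about 16%, while the rich schedule is within 2%. The direction held in every parameter set tried. The artefact enters pooled code 3, the contrast of codes 2 and 6, the AUC panels of Figure 13.4 and any dose-proportionality analysis. It enters code 4 only as far as its escalation subjects followed Table 7, because Protocol 7.4 lists Cohort 4 as sparse but gives cohorts enrolled under Amendment 1 the rich schedule. Code 5 is not mixed, since Tables 8 and 10 share PK times. Cmax is unaffected because every schedule samples 1 h after infusion.

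It also holds that first-dose AUC(0-inf) and CL cannot be compared between weekly and every-2-week columns. At 30 mg/kg, 29-52% of AUC(0-inf) is extrapolated, and one profile yields a CL of about 19 or 12.5-14.3 mL/h.

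The figures assume the Table 6 structure, 70 kg and nominal times. They show direction and order of size, not expected results. The consequence is a misleading description of a secondary endpoint, cheap to avoid.

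**What to change.** Amend SAP 13.2, 13.3 and the Figure 13.4 specification.

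1. Summarise and plot non-compartmental AUC(0-168) and AUC(0-tau) separately by sampling schedule, without pooling escalation and PK/PD subjects whose schedules differ. Base cross-dose and dose-proportionality comparisons on subjects with the 24 h and Day 4 samples, or on individual AUC from the population model.
2. Set one lambda-z window in advance, for example from 24 h on as in Protocol Table 5. Show the extrapolated percentage beside each AUC(0-inf), CL and t1/2, and flag highly extrapolated values. Do not compare non-compartmental AUC(0-inf) or CL across dosing intervals; use population-model estimates when that analysis is done.

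A fixed exclusion limit, such as 20% extrapolated, is not advised. With the last 3 points it would remove every AUC(0-inf) at 10 mg/kg (27-50% extrapolated) and at 30 mg/kg (29-52%). At 3 mg/kg it would keep sparse values (17.5% extrapolated, AUC(0-inf) 19% too high) and drop weekly ones (43%) that are within about 1%.

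The cost is SAP wording and some display programming; no new samples are needed. The downside is smaller numbers per displayed group. Code 2, being escalation only, also leaves the cross-dose AUC comparison unless model-based AUC is available.
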